Note: Baseline serum ALP and TBL should be established by at least 2 samples obtained at least 4 weeks and no more than 12 weeks apart. One sample can be obtained from the patient's medical history and 1 sample can be obtained during the Screening Period, or both samples can be obtained during the Screening Period. If the values of ALP or TBL in both samples are within normal ranges, the variability of the marker is assumed adequate for randomization. If the values of ALP or TBL are higher than normal values, the patient will be eligible for enrollment provided the increase from the first to second sample is $\leq 40\%$. If the values from sample 1 are higher than those from sample 2 (ie, there is a decrease), the patient will be eligible despite a $>40\%$ difference. A third sample can be collected if an increase from sample 1 to sample 2 exceeds the 40% limit. If sample 3 exceeds the 40% limit (compared to sample 1), this increase shall prompt the search for clinical signs or symptoms of liver impairment, and the patient will not be eligible for enrollment.

c. Liver stiffness compatible with liver fibrosis stage F2 or F3 determined by FibroScan[®] vibration-controlled transient elastography assessment cut-off value ≥ 8.5 kPa.

d. FibroScan controlled attenuation parameter (CAP) for steatosis with cut-off values >300 dB/m.

Note: Patients do not need to undergo a CAP assessment if their medical records indicate a magnetic resonance imaging (MRI)-proton density fat fraction (MRI-PDFF) LFC $\geq 10\%$ within 12 months prior to screening.

Note: Histology within 12 months prior to screening will supersede FibroScan entry criteria if the following criteria are met: NASH with fibrosis stage F2 to F3, defined as portal fibrosis with few septa (F2) or bridging septa between central and portal veins (F3), and nonalcoholic fatty liver disease (NAFLD) activity score ≥ 4 , including a minimum of 1 point each for ballooning and inflammation. However, if a patient participated in a previous study with a NASH investigational drug between 365 and 60 days prior to being screened for this study, the histology information will only be considered if the biopsy was performed after the end of the patient's participation in the previous study.

e. LFC $\geq 10\%$ as measured by MRI-PDFF.

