9. Has, in the opinion of the Investigator, clinically significant cardiovascular or cerebrovascular disease within 90 days prior to the first study drug administration, including, but not limited to, myocardial infarction, acute coronary syndrome, revascularization (percutaneous coronary intervention or coronary artery bypass grafting) or ischemic stroke, or implanted defibrillator or pacemaker.
10. Has participated in any drug study within 90 days prior to the first study drug administration in the current study.
11. Has had major surgery within 90 days prior to the first study drug administration in the current study.
12. Has a history of relevant drug and/or food allergies. The term "relevant" applies if any of the following allergy conditions are met:
 - a. Has had several episodes of drug-induced urticaria or other immediate allergic signs (eg, rhinoconjunctivitis, respiratory) (≥ 2 in total at whatever time in medical history and with 1 or several drugs).

- b. Has ongoing urticaria episodes (attributed to whatever allergen) or has other active history of immediate type reaction allergies (eg, allergic rhinoconjunctivitis, allergic asthma, or latex allergy).
- c. Has had a moderate or severe allergic reaction (\geq Grade 2 per the World Allergy Organization reference table, ie, urticaria alone with a Grade 1 is not relevant).
- d. Has any allergic condition that might require an emergency epinephrine injection (similar to the EpiPen[®] Auto-Injector).

13. Has a history of hypersensitivity to the study drug or to any of the excipients or placebo.

14. Unable to undergo an MRI-PDFF due to:

- a. Contraindication to MRI examination.
- b. Severe claustrophobia impacting ability to perform MRI during the study, despite mild sedation/treatment with a short half-life (ie, <20 hours) anxiolytic.
- c. Body weight or girth exceeding the scanner capacities.

15. Is using any of the following disallowed medications:

- a. Anticancer drug(s), immunomodulator(s), or immunosuppressant(s) within 90 days or 5 half-lives prior to screening, whichever is longer, or any drug historically associated with NAFLD for >2 weeks in the year prior to screening (eg, amiodarone, methotrexate, systemic glucocorticoids, tetracyclines, tamoxifen, estrogens at doses greater than those used for hormone replacement, anabolic steroids, or valproic acid or other known hepatotoxins at the Investigator or Medical Monitor's discretion).

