- b. Vitamin E (>400 IU/day), glitazones, glucagon-like peptide-1 receptor agonists, ursodeoxycholic acid, or obeticholic acid within 90 days prior to screening.
- c. Agents (including herbal over-the-counter weight loss preparations) or medications known to significantly impact body weight within 90 days prior to screening (eg, sibutramine, phentermine, and orlistat).
- d. Bile acid sequestrants (eg, cholestyramine) or lipid-modifying agents (eg, fibrates or ezetimibe) other than rosuvastatin, atorvastatin, simvastatin, pravastatin, fluvastatin, or lovastatin.
- e. Agents that are substrates for cytochrome P450 (CYP) 2C8 or CYP2C9 and have a narrow therapeutic index (eg, warfarin).

16. Has prior or planned (during the study period) bariatric surgery (eg, gastroplasty or Roux-en-Y gastric bypass).

17. Has type 1 diabetes mellitus.

18. Has type 2 diabetes mellitus (T2DM) and hemoglobin A1c $>9.5\%$ or has not been on a stable dose of antidiabetic medication for at least 90 days prior to screening.

19. Has had total body weight loss of $>5\%$ within 6 months or since a liver biopsy, if applicable.

20. Has any of the following exclusionary laboratory results at screening:

- a. ALT $>5 \times$ ULN, AST $>5 \times$ ULN.
- b. International normalized ratio ≥ 1.3 , unless on anticoagulant therapy.
- c. Platelet count $<$ lower limit of normal.
- d. Estimated glomerular filtration rate $<50 \text{ mL/min/1.73 m}^2$ (the Modification of Diet in Renal Disease formula).
- e. Creatine kinase (CK) $>$ ULN in patients on concomitant statin therapy and CK $>3 \times$ ULN in all other patients.
- f. Thyroid-stimulating hormone $>1.5 \times$ ULN or abnormal free triiodothyronine or free thyroxine.

Note: Unless otherwise specified, repeat testing may be performed in consultation with the Medical Monitor if any of the above laboratory abnormalities are found.

21. Has history of clinically significant gastrointestinal disease (especially: cholecystectomy prior to age 25 years, peptic ulcerations, gastrointestinal bleeding, inflammatory bowel disease, or bariatric surgery); renal, hematologic, endocrine, oncologic, pulmonary, immunologic, or cardiovascular disease; neurologic or psychiatric disease (including any use of addictive substances such as regular opioid treatment and/or any use of illicit drugs); or any other condition, which, in the opinion of the Investigator, would jeopardize the safety of the patient or impact the validity of the study results.

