22. Has a body mass index $>45 \text{ kg/m}^2$.

STUDY DESIGN AND DURATION:

This is a 2-part, randomized, double-blind, multicenter, placebo-controlled study to evaluate the safety and efficacy of EYP001a in patients with NASH who likely have stage F2 to F3 fibrosis at approximately 50 global clinical sites. Overall, approximately 114 eligible patients will be enrolled: 24 patients in Part A (Safety Run-in Cohort), followed by 90 patients in Part B.

In Part A, 24 patients will be randomized on Day 1 to 1 of 4 parallel treatment groups: 100 mg EYP001a twice daily (BID), 200 mg EYP001a once daily (QD), 400 mg EYP001a QD, or placebo BID. In Part B, 90 patients will be randomized on Day 1 to 1 of 3 parallel treatment groups: 100 mg EYP001a QD, 200 mg EYP001a QD, or placebo QD.

Randomization will be stratified by statin use (yes, no) and T2DM status (yes, no) at screening in Part A, and by statin use (yes, no) and LFC (stratification factor with 3 categories: LFC $<16\%$, $16\% \leq LFC < 22\%$, and $22\% \leq LFC$) in Part B at screening.

The following sequence of screening procedures will be applied to each patient who signs an informed consent form: 1) eligibility based on clinical and biological inclusion and exclusion criteria; 2) eligibility based on FibroScan criteria as described in [Inclusion Criterion 3](#); and 3) confirmation of eligibility based on MRI-PDFF results. A patient who is first designated as a screen failure prior to being randomized may be rescreened upon Sponsor or designee approval. If the patient was screen failed after the MRI-PDFF was completed, the original MRI-PDFF scan may be utilized for rescreening, provided it was obtained within 1 month prior to rescreening.

Part A (Safety Run-in Cohort)

Participation in Part A of the study will consist of a Screening Period (up to 12 weeks prior to Day 1), a 12-week Treatment Period, and a Follow-up Visit at Week 14; total study duration is up to 182 days. All eligibility criteria must be confirmed prior to dosing on Day 1.

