1 INTRODUCTION AND BACKGROUND INFORMATION

Nonalcoholic steatohepatitis (NASH) is the most common chronic liver disorder in western countries and involves steatosis, defined as liver fat content (LFC) >5%, leading to inflammation with hepatocyte injury. It is estimated that more than 5% of the population has advanced NASH. Its main consequence is liver fibrosis, which can progress to cirrhosis and hepatocellular carcinoma. Currently no registered drug therapy exists for this disease, which represents an important challenge.

Clinical studies show evidence linking liver fat improvements in NASH with histological improvements. A study with ezetimibe for 24 weeks showed that histologic responders had approximately 30% relative LFC reduction on magnetic resonance imaging (MRI)-proton density fat fraction (MRI-PDFF) relative to a 2% increase for nonresponders.¹ Findings in the FLINT study with farnesoid X receptor (FXR) agonist obeticholic acid showed that with reductions in LFC of $\geq 30\%$, there were greater odds of histologic response based on 2-point nonalcoholic fatty liver disease (NAFLD) activity score reduction.²

A randomized, double-blind, placebo-controlled study with recombinant injected fibroblast growth factor 19 (FGF19) drug NGM282 for 12 weeks showed robust efficacy with -9.7% to -11.9% significant absolute LFC changes assessed via MRI-PDFF, as compared to -0.9% for placebo.³ An extension of this main study with a small group of patients (n = 22) who were assessed with paired MRI-PDFF and liver histology at baseline and Week 12⁴ adds to the growing body of evidence showing how improvements in LFC may translate into histological changes.

Improvements in liver histology are accepted surrogate endpoints for registration studies because they eventually translate to lower rates of liver transplant and liver disease progression. While there have not been enough studies conducted to demonstrate with scientific certainty that improvements in LFC assessed by noninvasive measurements, like MRI-PDFF, lead to clinically relevant outcomes, MRI-PDFF is an accepted endpoint of early stage proof-of-concept NASH studies.

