3.1.3 Definition of Baseline

Baseline for the imaging parameters (LFC, cT1, liver stiffness measurement [LSM] and controlled attenuation parameter [CAP]) will be defined as the value obtained at the Screening Visit.

Baseline for ALT, AST, Total Bilirubin and alkaline phosphatase (ALP) will be defined as the average of all pre-dose values (i.e. those taken during the Screening Period and on Day 1 as assessed by the central laboratory). Only assessments taken within 12 weeks prior to Day 1 will be considered in the average calculation.

Baseline for the AST/ALT Ratio will be calculated using the derived baseline values for ALT and AST as described above.

Baseline for the other efficacy and safety variables will be defined as the last available value obtained up to the first dose of study drug.

For patients randomized and not treated, the baseline value will be the last available value on or before the day of randomization.

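### The 90-day prior-drug-study interval is counted to first dose, but baseline LFC is a screening scan that may be taken 84 days or more before it

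*Protocol*

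**What the plan says.** **Prior drug studies.** Exclusion Criterion 10 (Protocol Synopsis and Section 4.3) excludes a patient who "Has participated in any drug study within 90 days prior to the first study drug administration in the current study". The interval runs back from Day 1.

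**Baseline.** SAP Section 3.1.3 states that baseline for the imaging parameters, LFC among them, "will be defined as the value obtained at the Screening Visit". Protocol Section 3.1 (Efficacy Assessments) agrees. Participation "will consist of a Screening Period (up to 12 weeks prior to Day 1"), and the Part B schedule in Appendix A gives the window as Day -84 to Day -3. Section 4.1 also allows a scan from a failed screening to be reused if it is no more than 1 month old at rescreening.

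**Other washouts.** Criterion 15b covers named drugs, ending with "ursodeoxycholic acid, or obeticholic acid within 90 days prior to screening". Criterion 15c uses the same 90 days before screening for weight-affecting agents.

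**Lipid drugs.** Criterion 15d disallows current use of "Bile acid sequestrants (eg, cholestyramine) or lipid-modifying agents (eg, fibrates or ezetimibe) other than rosuvastatin, atorvastatin, simvastatin, pravastatin, fluvastatin, or lovastatin", with no look-back, and Section 5.6.1 repeats the list. Section 5.6.2 nevertheless provides for patients on other lipid-lowering drugs to stay in the trial if they have been stable for at least 90 days before first dose and remain so.

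**The concern.** The purpose of a washout here is to keep earlier drug effects out of the measurements. For the primary endpoint the first of those measurements is the screening scan, not Day 1. An interval that ends at Day 1 leaves an unprotected stretch before the scan, and that stretch is longest for patients scanned early.

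The case is not far-fetched. The histology note in Inclusion Criterion 3 sets a condition "if a patient participated in a previous study with a NASH investigational drug between 365 and 60 days prior to being screened", so the protocol expects some candidates to come from NASH drug trials as recently as 60 days before screening. Section 1 also shows that such agents move LFC: an injected FGF19 drug changed it by -9.7 to -11.9 points over 12 weeks, against -0.9 on placebo. That drug is not named in Criterion 15b, so Criterion 10 is the only rule that sets a washout for it.

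If LFC is still lowered at baseline and rebounds during the 12 weeks, the change score for that patient is displaced upwards whatever the assigned arm. The absolute change and every responder criterion inherit this. The Per-Protocol analysis would not remove such a patient, because meeting Criterion 10 as written is not a violation.

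**Working it through.** **1. The plan's own figure.** Protocol Section 10.2.8 gives a difference of 5.1 points, SD 5.8, one-sided alpha 0.0125 per comparison, power 0.80, 26 completers and 30 randomised per arm.
- Z formula: n = 2 × [5.8 × (2.2414 + 0.8416) / 5.1]² = 24.6, rounded up to 25.
- A t-test calculation gives 78.4% power at 25 and 80.2% at 26, so 26 is the t-test figure.
- 26 / (1 - 0.13) = 29.9, rounded up to 30.
- Z-test power at 26 = Φ(5.1 / (5.8 × √(2/26)) - 2.2414) = 82.4%. This is the reference below.

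**2. Timing.** Minimum gap from the end of prior-study participation to the scan = 90 - (days from scan to first dose).

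| Scan | Days before first dose | Minimum gap (days) |
|---|---|---|
| Day -84 | 84 | 6 |
| Day -56 | 56 | 34 |
| Day -28 | 28 | 62 |
| Day -3 | 3 | 87 |
| Reused at rescreening | 84 + 30 = 114 | -24 |

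A negative gap means that the scan could fall inside the earlier study. With 90 days counted back from screening, every scan taken in that screening period has a gap of at least 90 days. A reused scan would not, because it precedes rescreening.

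**3. Possible effect on precision.** The documents give neither the share f of affected patients nor the rebound R. Both are assumptions.
- Section 1.2.2 reports a Part A LFC reduction of 6.3 points, or 35.3%. The implied baseline is 6.3 / 0.353 = 17.8%.
- Section 1 says "A study with ezetimibe for 24 weeks showed that histologic responders had approximately 30% relative LFC reduction". Taking 30% of 17.8 gives R = 5.4 points.
- SD' = √(5.8² + f(1 - f) × 5.4²); power = Φ(5.1 / (SD' × √(2/26)) - 2.2414).

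| f | SD' | Power | Shift in every arm's mean (f × R) |
|---|---|---|---|
| 0 | 5.80 | 82.4% | 0 |
| 5% | 5.92 | 80.7% | 0.27 |
| 10% | 6.02 | 79.2% | 0.54 |
| 20% | 6.19 | 76.7% | 1.08 |

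Varying R from 2 to 6 points over the same shares gives power from 82.1% (5%, 2 points) to 75.4% (20%, 6 points). The expected difference between arms does not change in any row.

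**4. Chance imbalance.** Three affected patients in one arm of 26 move its mean by 3 × 5.4 / 26 = 0.62 point. The standard error of a difference is 5.8 × √(2/26) = 1.61, so this is about 0.4 standard errors. It is the same variation already counted in SD', not an additional loss.

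**The case against.** Most of the case on the other side concerns size, and much of it stands.

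- **Six days is an extreme.** MRI is the last screening step, after clinical, laboratory and FibroScan eligibility, so few scans will be near Day -84. Criterion 10 counts participation rather than last dose, so off-drug follow-up in the earlier trial lengthens the true washout. Both points stand. Even so, a Day -28 scan is guaranteed only 62 days, and a reused scan is guaranteed nothing.
- **Much is already covered.** Criteria 15a to 15c require at least 90 days before screening for obeticholic acid, glitazones, GLP-1 agonists, vitamin E above 400 IU/day, immunomodulators and weight-affecting agents, and Criterion 19 excludes recent weight loss above 5%. The remaining gap under Criterion 10 is unlisted investigational drugs.
- **The anchor is internally consistent.** Criteria 9 to 11 all count from first dose. That suits the cardiovascular and surgical criteria, which protect patients during dosing. It does not suit a criterion that also has to protect a scan.
- **The power figures are assumed.** The 30% fall is from ezetimibe histologic responders only, full rebound within 12 weeks is assumed, and adjustment for baseline LFC is ignored. This stands. The adjustment may absorb some of the noise, but it cannot identify who will rebound.

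Three stronger readings are tempting, and the documents do not support them.
- A reader might infer that a patient who left a NASH trial 6 to 59 days before screening escapes the histology note. The note turns on having participated between days 365 and 60, not on having left then, so anyone whose participation reached back to day 60 is covered. It also governs only whether a biopsy replaces FibroScan; an MRI-PDFF LFC of at least 10% is still required.
- A reader might infer damage from misplacement in the LFC strata. The strata are defined by the screening value itself, and SAP Sections 3.4.1.1 and 5 drop the stratum from the primary model.
- A reader might infer that Criterion 15d simply lacks a 90-day look-back. While Section 5.6.2 provides for patients on other lipid-lowering drugs to continue, the documents do not establish which rule is intended.

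**Conclusion.** The concern holds as a mismatch of anchors. Criterion 10 guarantees 90 days before first dose but only 6 days before the earliest permitted scan, and none before a reused one, whereas Criteria 15b and 15c count from screening.

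The consequence is limited. A reader might infer a biased drug-placebo comparison, but eligibility is settled before randomisation and is the same for all arms, so the effect is non-differential in expectation. The cost is added variance, chance imbalance in small arms, and a drift in within-arm changes and responder rates.

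The size cannot be determined from the documents. With a 5.4-point rebound, power stays at or close to the planned 80% if 5% to 10% of patients are affected and falls to 76.7% at 20%. The change is worth making because it is cheap and protects the primary baseline, not because a large loss has been shown.

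The contradiction between Criterion 15d with Section 5.6.1 and Section 5.6.2 is a separate finding and does not depend on these assumptions.

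**What to change.** 1. In Criterion 10 (Synopsis and Section 4.3), count the 90 days back from screening, as Criteria 15b and 15c do. Where an earlier MRI-PDFF is reused at rescreening, count from the date of that scan.
2. Reconcile Criterion 15d and Section 5.6.1 with Section 5.6.2 on non-statin lipid-modifying drugs, and state how the reconciled rule is timed relative to the baseline scan. Which rule applies is for the sponsor to decide.

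The first change is wording only and needs no new procedure. A few candidates coming from another trial would wait up to about 12 weeks longer before screening. It helps only patients not yet screened; SAP Section 4.1 records the second Part B interim as completed in February 2021.

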AUDIT	Alcohol Use Disorders Identification Test
AUDIT-C	Alcohol Use Disorders Identification Test-Concise
BID	Twice daily
BMI	Body mass index
C4	7 α hydroxy-4-cholesten-3-one
CAP	Controlled attenuation parameter
CFR	Code of Federal Regulations
CK	Creatine kinase
C _{max}	Maximum observed plasma concentration
CRA	Clinical Research Associate
cT1	Iron-corrected T1
CTA	Clinical trial authorization
CTCAE	Common Terminology Criteria for Adverse Events
CYP	Cytochrome P450
DSMC	Data Safety Monitoring Committee
ECG	Electrocardiogram
eCRF	Electronic case report form
EDC	Electronic data capture
eGFR	Estimated glomerular filtration rate
EIU	Exposure in Utero
EOS	End of Study
ET	Early Termination
FDA	Food and Drug Administration
FGF19	Fibroblast growth factor 19
FXR	Farnesoid X receptor
GCP	Good Clinical Practice
GGT	Gamma-glutamyltransferase
HBV	Hepatitis B virus
hCG	Human chorionic gonadotropin
HCV	Hepatitis C virus
HCV Ab	Hepatitis C virus antibody

Abbreviation	Definition
HIV	Human immunodeficiency virus
ICF	Informed consent form
ICH	International Council on Harmonisation
IEC	Independent Ethics Committee
IRB	Institutional Review Board
IRT	Interactive Response Technology
ITT	Intent-to-Treat
LDL-C	Low-density lipoprotein cholesterol
LFC	Liver fat content
LOD	Limit of detection
LSM	Liver stiffness measurement
MDRD	Modification of Diet in Renal Disease
MedDRA	Medical Dictionary for Regulatory Activities
mITT	Modified Intent-to-Treat
MRI	Magnetic resonance imaging
MRI-PDFF	Magnetic resonance imaging-proton density fat fraction
NAFLD	Nonalcoholic fatty liver disease
NASH	Nonalcoholic steatohepatitis
PD	Pharmacodynamic(s)
PK	Pharmacokinetic(s)
po	Orally
QD	Once daily
RNA	Ribonucleic acid
SAE	Serious adverse event
SUSAR	Suspected unexpected serious adverse reaction
T2DM	Type 2 diabetes mellitus
TBL	Total bilirubin
TEAE	Treatment-emergent adverse event
T _{max}	Time to reach the maximum observed plasma concentration
ULN	Upper limit of normal
VCTE	Vibration-controlled transient elastography
WHO	World Health Organization
WHR	Waist to hip ratio
WHR	Waist to height ratio

1 INTRODUCTION AND BACKGROUND INFORMATION

Nonalcoholic steatohepatitis (NASH) is the most common chronic liver disorder in western countries and involves steatosis, defined as liver fat content (LFC) >5%, leading to inflammation with hepatocyte injury. It is estimated that more than 5% of the population has advanced NASH. Its main consequence is liver fibrosis, which can progress to cirrhosis and hepatocellular carcinoma. Currently no registered drug therapy exists for this disease, which represents an important challenge.

Clinical studies show evidence linking liver fat improvements in NASH with histological improvements. A study with ezetimibe for 24 weeks showed that histologic responders had approximately 30% relative LFC reduction on magnetic resonance imaging (MRI)-proton density fat fraction (MRI-PDFF) relative to a 2% increase for nonresponders.¹ Findings in the FLINT study with farnesoid X receptor (FXR) agonist obeticholic acid showed that with reductions in LFC of $\geq 30\%$, there were greater odds of histologic response based on 2-point nonalcoholic fatty liver disease (NAFLD) activity score reduction.²

A randomized, double-blind, placebo-controlled study with recombinant injected fibroblast growth factor 19 (FGF19) drug NGM282 for 12 weeks showed robust efficacy with -9.7% to -11.9% significant absolute LFC changes assessed via MRI-PDFF, as compared to -0.9% for placebo.³ An extension of this main study with a small group of patients (n = 22) who were assessed with paired MRI-PDFF and liver histology at baseline and Week 12⁴ adds to the growing body of evidence showing how improvements in LFC may translate into histological changes.

Improvements in liver histology are accepted surrogate endpoints for registration studies because they eventually translate to lower rates of liver transplant and liver disease progression. While there have not been enough studies conducted to demonstrate with scientific certainty that improvements in LFC assessed by noninvasive measurements, like MRI-PDFF, lead to clinically relevant outcomes, MRI-PDFF is an accepted endpoint of early stage proof-of-concept NASH studies.

EYP001a is an agonist of the FXR, a key regulator of bile, lipid, and glucose metabolism, currently under clinical investigation as a new therapy for a functional cure of chronic hepatitis B virus (HBV) infection. In an experimental rodent model of NASH,⁵ EYP001a analogue def2572 has been shown to reduce liver steatosis, inflammation, apoptosis, and fibrosis. Moreover, FXR activation with the bile improved the histological features of NASH in patients with noncirrhotic NASH.²

[figure not shown]
